2.4.3 Medical history

Relevant medical history and current medical conditions will be tabulated by system organ class (SOC) and PT of the Medical Dictionary for Regulatory Activities (MedDRA) dictionary (version 19.1 or a more recent version) for the FAS. The SOCs will be presented in alphabetical order. PTs will be sorted by decreasing proportion and alphabetical order.

Furthermore, medical history data will be listed by center and patient number for the FAS.

2.5 Treatments (study treatment, rescue medication, concomitant therapies, compliance)

Unless otherwise stated, all analyses will be based on patients in the Safety Set.

2.5.1 Study treatment/compliance

Study treatment

Definitions of duration of exposure, total patient-years exposure, average daily dose, cumulative total dose as well as percentage of planned dose taken are defined in the following table (Table 2-3).

Table 2-3 Study drug exposure

Term	Definition
Overall drug exposure (days)	[(date of last administration of study treatment) – (date of first administration of study treatment) + 1]
Drug exposure on dose X (days)	[(date of last administration of study treatment on dose X) – (date of first administration of study treatment on dose X) + 1]
Average dose (planned [mg/kg/day] or actual [mg/kg/day]	Mean dose over all days between first and last dose, including interruptions: sum of all (X dose × corresponding drug exposure on dose X) / overall drug exposure

Term	Definition
Final dose (planned [mg/kg/day] or actual [mg/kg/day])	Last non-zero dose record
Cumulative dose (planned [mg/kg] or actual [mg/day])	Sum of daily doses over all days between first administration of study treatment and last administration of study treatment
Total patient-years (years)	Overall duration of exposure (days) / 365.25
Percentage of planned dose taken (%)	100 × (Cumulative actual dose [mg/kg] / Cumulative planned dose [mg/kg])

Note:

- (1) The actual dose will be adjusted for the current weight (kg). The current weight is the weight prior or on the date of the start of each dosage record. If there are multiple weight assessments taken on the same day, then the mean value of these records will be used for the current weight.
- (2) Cumulative dose is the sum of daily doses hence day is not part of the unit.

Descriptive statistics for the number of days a patient was on study treatment will be provided for the Safety Set. The table will also provide the total patient-years that all patients were on treatment. The frequency and percentage of patients belonging to each categorical range of exposure weeks will be provided (see Table 2-1 for definition of study period categories).

In addition, summary statistics (frequency and percentage of patients for categorial variables; descriptive statistics for continuous variables) of dosage will be provided for:

Categorical variables

- average planned dose ($< 10.5, 10.5 \text{ to} < 17.5, 17.5 \text{ to} < 24.5, <math>\ge 24.5 \text{ mg/kg/day}$)
- average actual dose ($< 10.5, 10.5 \text{ to} < 17.5, 17.5 \text{ to} < 24.5, <math>\ge 24.5 \text{ mg/kg/day}$)
- final planned dose (< 10.5, 10.5 to < 17.5, 17.5 to < 24.5, \geq 24.5 mg/kg/day)
- final actual dose ($< 10.5, 10.5 \text{ to} < 17.5, 17.5 \text{ to} < 24.5, <math>\ge 24.5 \text{ mg/kg/day}$)

Continuous variables

- average planned dose (mg/kg/day)
- average actual dose (mg/kg/day)
- final planned dose (mg/kg/day)
- final actual dose (mg/kg/day)
- cumulative planned dose (mg/kg)
- cumulative actual dose (mg/kg)
- percentage of planned dose taken (%)
- duration of actual dose (days)
 - The duration of actual dose refers to the number of days in the study where actual dose is non-zero.
- relative duration of actual dose (%)
 - The relative duration of actual dose is defined as the ratio of duration of actual dose (days) to overall drug exposure (days).

Futhermore, the frequency and percentage of patients with dose decreases, increases in planned dose, or dose interruptions, the corresponding reasons, and average length of dose interruptions will be summarized. A shift table to compare final planned dose to final actual dose will also

be provided. A planned dose reduction is when a planned dose is lower than the previous planned dose, a planned zero dose is included as a dose reduction record. A planned dose increase is when a planned dose is higher than the previous planned dose. Patients with more than one reason for planned dose change are counted once per reason in each category (reduction or increase). A dose interruption is when an actual dose is recorded as zero.

Average actual daily dose will be also graphically presented using a box plot over time (see Table 2-1 for study period definition).

Study treatment data will be listed by center and patient number for the Safety Set.

Study compliance

The patient compliance with DFX FCT will be evaluated using the count of DFX FCT by the relative consumed tablet count (%). The relative consumed tablet count is defined as the ratio of total count consumed to total count prescribed, where

- Total count consumed is derived from cumulative dispensed and returned counts:
 The total count consumed is calculated as the sum of counts dispensed minus the sum of counts returned.
- Total count prescribed is cumulative prescribed count:

The prescribed count corresponds to the count prescribed by the investigator for the period that the patient should have taken the study treatment during this period. For each strength (90 mg, 180 mg, and 360 mg tablets), the prescribed count for a period is calculated from the daily prescribed count at the beginning of this period multiplied by the duration (days) of this period. The daily prescribed count is the sum of counts prescribed per strength. The duration of a period will be calculated using the following formula:

(end date of the period) - (start date of the period) + 1

The subsequent period duration calculation will exclude the start day (i.e., a day will be not be counted in subsequent periods). The total count prescribed is the sum of counts prescribed over all periods.

If a patient does not return the study drug, the compliance will not be calculated.

Descriptive statistics including 95% confidence interval (CI) for the mean relative consumed tablet count will be provided.

In addition, the persistence of DFX FCT will be summarised at Month 3, Month 6, Month 9, and Month 12. Persistence is defined as the continuous use of DFX FCT without a gap of \geq 30 or \geq 60 days over a fixed time interval of interest. A gap will be calculated as the time between two consecutive dates of study drug administration when study drug was administered (i.e. actual dose is non-zero) within the fixed time interval of interest.

Furthermore, a listing will be provided including dispensed/returned and prescribed counts as well as the relative consumed tablet count by center and patient number for the Safety Set.

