6.3.1.2 Elevations in serum creatinine

Serum creatinine should be monitored during the study as stated in the visit evaluation schedule in Table 7-1.

In case of a single increase in serum creatinine, the assessment will be repeated at the next visit, or as clinically indicated.

A deferasirox dose reduction of 7 mg/kg/day for the FCT should be performed if there is a rise in serum creatinine of 33% above Baseline value (average of Visit 1 and 2) resulting in a serum creatinine above the ULN on 2 consecutive visits (a minimum of 7 days apart).

If after a dose reduction, a progressive increase in serum creatinine beyond the ULN is observed, a treatment interruption is recommended.

After a treatment interruption, if serum creatinine falls below the age appropriate ULN on 2 consecutive visits, it is recommended to resume therapy at 50% of the last dose, and after 1 month, if the serum creatinine increase does not recur, study medication can be returned to 100% of the last dose (including body weight adjustment if required).

Use of deferasirox is contraindicated in patients with estimated creatinine clearance less than 60 mL/min.

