6.3.1.5 Skin rash

For skin rash of mild/moderate severity (defined as those causing minimal symptoms, which require no supportive treatment or minimal supportive treatment), study drug should be continued without dose adjustment. The skin rash may resolve spontaneously without further intervention.

If the rash persists for > 1 week or becomes more severe, treatment with study drug will be interrupted. After the rash resolves, the study drug should be resumed at 50% of the patient's last dose and if the rash does not recur, the dose should be increased back to 100% of the patient's dose after 2 weeks.

For a severe rash (distressing symptoms requiring discontinuation and/or systemic steroids), treatment should be discontinued until resolution of rash. Once the rash has resolved, treatment should be resumed at 50% of the patient's dose. If necessary, a brief course of oral steroids may be given concurrently with resumption of study drug. If the rash does not recur, treatment should be increased by steps of 3.5 mg/kg/day for deferasirox FCT every 2 weeks until the patient's last dose is achieved.

If the rash recurs, study treatment may be discontinued if the investigator believes that it is in the best interest of the patient. Novartis may be contacted by the investigator to discuss dosing options if the investigator so desires.

Other skin disorders

Severe cutaneous adverse reactions, including Stevens-Johnson syndrome, toxic epidermal necrolysis and drug reaction with eosinophilia and systemic symptoms have been reported during Exjade therapy. If any severe cutaneous adverse reactions is suspected, study treatment must be immediately discontinued and not be reintroduced.

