10.3 Treatments (study treatment, concomitant therapies, compliance)

The following variables will be summarized with descriptive measures for the Safety Set: duration of exposure (at intervals as described in the Statistical Analysis Plan); average planned (mg/kg/day) and average actual daily dose (mg/day); cumulative planned (mg/kg) and total actual dose (mg); percentage of planned dose taken; frequency of interruptions,

decreases and increases in planned dose overall and by reason for change as recorded in the eCRF.

The total patient-years while on treatment, calculated as the sum of (overall drug exposure)/365.25 will be provided.

The duration of exposure is defined as the number of weeks between the start and end of study medication. The end of study medication day is the last day with a non-zero actual dose of study medication as recorded on the drug administration pages.

The average daily dose (planned or actual) is calculated as the mean dose over all days between first and last dose, including interim days with zero dose (interruptions). The cumulative dose is calculated as the sum over the daily doses of all days between first and last dose. The current weight is used when calculating the actual daily dose.

The percentage of planned dose taken is derived as $100 \times \text{cumulative}$ actual dose (mg)/cumulative planned dose (mg/kg).

Prior and concomitant medications and significant non-drug therapies will be summarized using frequency tables according to WHO Anatomical Therapeutic and Chemical class and WHO generic term. Prior medications are defined as drugs taken prior to the first dose of study medication. Concomitant medications are medications taken between the first and last day with study medication, excluding medications started on the last day of study medication. Medications which start prior to the first dose of study medication and continue thereafter are counted in both summaries.

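### As written, SAP Table 2-3 counts the days between two spells on one dose level at that level, so average dose contradicts the cumulative-dose row; the average-actual-dose subgroup also needs an interpretive footnote

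*SAP*

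**What the plan says.** **Formula.** SAP Table 2-3 (section 2.5.1) gives exposure on dose X as the last date on X minus the "date of first administration of study treatment on dose X", plus 1. The average-dose row, for planned and actual dose alike, describes itself as "Mean dose over all days between first and last dose, including interruptions". It then computes the sum of X times the "corresponding drug exposure on dose X", divided by overall drug exposure. The cumulative-dose row is "Sum of daily doses over all days between first administration of study treatment and last administration of study treatment". Note (1) says of the weight adjustment: "The current weight is the weight prior or on the date of the start of each dosage record". Protocol 10.3 also takes the mean over all days from first to last dose, "including interim days with zero dose (interruptions").

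**Return to an earlier level.** After a creatinine-driven interruption and a month at half dose, Protocol 6.3.1.2 says that "study medication can be returned to 100% of the last dose". After a rash and two weeks at half dose, Protocol 6.3.1.5 says that "the dose should be increased back to 100"%. Protocol 6.3.1.3 allows steps of 3.5 or 7 mg/kg/day in response to ferritin, every 3 months. SAP 5.1.4.2 shows that the planned dose itself can be recorded as zero.

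**Subgroup.** SAP 2.2.1 groups patients by actual average daily dose (<7, 7 to <21, >=21 mg/kg/day). SAP 2.6.4 tabulates overall AEs, serum creatinine and creatinine clearance by that group. Protocol 6.3.1 recommends reductions or interruptions for intolerance, and 6.3.1.2 prescribes a 7 mg/kg/day reduction after a confirmed creatinine rise.

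**The concern.** A first-to-last span equals the days spent on a level only if the patient never leaves it and comes back. Otherwise the gap is credited to X, and any other non-zero dose given in the gap is counted as well. The exposures by level can then add up to more days than the patient was treated, and the average multiplied by overall exposure no longer equals the cumulative dose in the same table. The average dose feeds the continuous and categorical dose summaries in SAP 2.5.1.

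The second issue is independent of the formula and remains once it is repaired. Average actual dose is measured after baseline over the whole treatment period, and some of the outcomes tabulated by it cause the dose to be lowered. Part of any difference between dose groups would therefore reflect how patients came to be in them.

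**Working it through.** The documents report no average dose to reproduce. The check is the identity that Table 2-3 should satisfy: average dose x overall exposure = cumulative dose.

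- Correct average = sum of daily doses / overall days.
- Formula average = sum over distinct non-zero levels of X x (last day on X - first day on X + 1) / overall days.

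A 24-month course is taken as 672 days (24 months of 4 weeks, the SAP's convention) or 730 calendar days. The dose sequences follow protocol rules. Interruption lengths and event dates are assumed. The two weeks at half dose after rash and the month (30 days) at half dose after a creatinine interruption come from Protocol 6.3.1.5 and 6.3.1.2.

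**Where the two agree.** Constant 21 gives 21.0 both ways. A one-way change, 21 for 168 days then 14 for 504, gives (3,528 + 7,056)/672 = 15.75 both ways.

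**Where they part** (planned dose, mg/kg/day):

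| Course | Correct | Formula |
|---|---|---|
| Rash: 21-0 (14 d)-10.5 (14 d)-21, 730 d | (702 x 21 + 14 x 10.5)/730 = 14,889/730 = 20.40 | (730 x 21 + 14 x 10.5)/730 = 15,477/730 = 21.20 |
| Rash: 28-0 (14 d)-14 (14 d)-28, 672 d | (644 x 28 + 14 x 14)/672 = 18,228/672 = 27.13 | (672 x 28 + 14 x 14)/672 = 19,012/672 = 28.29 |
| Ferritin: 17.5-14 (84 d)-17.5, 672 d | (588 x 17.5 + 84 x 14)/672 = 11,466/672 = 17.06 | (672 x 17.5 + 84 x 14)/672 = 12,936/672 = 19.25 |
| Temporary increase: 21-28 (84 d)-21, 672 d | (588 x 21 + 84 x 28)/672 = 14,700/672 = 21.88 | (672 x 21 + 84 x 28)/672 = 16,464/672 = 24.50 |
| Creatinine: 28 (300 d)-21 (28 d)-0 (30 d)-10.5 (30 d)-21 (284 d), 672 d | (8,400 + 588 + 315 + 5,964)/672 = 15,267/672 = 22.72 | (8,400 + 372 x 21 + 315)/672 = 16,527/672 = 24.59 |

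In the first row the exposures by level total 730 + 14 + 14 - 14 = 744 days if the zero-dose spell is left out, or 758 if it is counted as its own level, against 730 days treated. If the planned dose is left at 21 during that interruption, the figures are 15,183/730 = 20.80 against 21.20. In the second row the formula average exceeds every dose given. The third row crosses from the 10.5 to <17.5 category to 17.5 to <24.5. The creatinine row takes the last dose to be the 21 given before the interruption.

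**Limit for actual dose.** Take 1,260 mg at 60 kg (21.0) for 168 days, 28 days off, then 1,260 mg at 61 kg (20.66) for 476 days. The two spells have different X values and do not overlap. The average is 13,360/672 = 19.88 both ways.

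**Subgroup illustration, 60 kg only.** Planned 21 is 1,260 mg = 21.0 mg/kg (Table 14-6), and planned 14 is 810 mg = 13.5 mg/kg (Table 14-4). A permanent cut after day t gives (21t + 13.5(672 - t))/672, which is 13.81 at t = 28 and 20.69 at t = 644. At this weight the cut puts the patient in 7 to <21; without it the patient is in >=21. At other weights rounding matters: under Table 14-6, 16 of the 41 whole-kilogram weights from 40 to 80 kg give less than 21 mg/kg on planned 21 with no event at all.

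**The case against.** **Dose X may mean one dosing record.** The Dosage Administration Record holds start and end dates for each dose, the final-dose row and note (1) speak of records, and the average-dose row opens with a correct verbal definition. Programmed by record, the error does not arise. That stands as a plausible intention. But the exposure row does not mention records, note (1) ties only the weight to them, and the formula taken literally contradicts the words beside it.

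**The subgroup uses actual dose, where weight differences remove the overlap.** This also stands. A reader might infer that the formula misassigns patients to the dose subgroups. That is possible where the mg/kg value is identical before and after the gap, but the documents do not show that it will happen or how often.

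**Who is affected.** A reader might infer that every interrupted patient is overstated, and only those. Neither is so: one-way changes are computed correctly, and temporary increases are inflated too. A reader might also expect a creatinine event to push the average above the protocol maximum of 28. Protocol 6.3.1.2 places a reduction before any interruption, and the path worked above gives 24.59; the excess over 28 arises on the rash path.

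**The subgroup analysis is descriptive and supportive.** The SAP tests no hypothesis and nowhere calls the split a dose-response comparison. It also plans tables of AEs requiring dose change, dose changes by reason, a box plot of actual dose over time, and listings with AE onset dates. This limits the remedy to a footnote. It does not remove the need for one, because none of these outputs tells the reader of the subgroup table that events influence group membership.

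**Conclusion.** The formula in Table 2-3 is wrong as written for any patient who resumes an earlier dose level with the same X value. In the worked courses the overstatement runs from 0.80 (21.20 against 20.40) to 2.62 mg/kg/day (24.50 against 21.88). It can change the reporting category or exceed every dose given. These sizes rest on assumed timings, and the number of patients affected cannot be derived. The point mainly concerns average planned dose.

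Percentage of planned dose taken is built from cumulative doses and is unaffected, as is the primary overall AE incidence. A reader might infer that the safety conclusions are compromised; the documents do not support that.

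The secondary point holds as one of interpretation. Average actual dose is partly a consequence of the AEs and creatinine rises tabulated by it, only partly because dose also moves with ferritin and with tablet rounding. The size of the effect, and any resulting gap between groups, cannot be derived from the documents. The 60 kg figures show the mechanism at that weight and do not generalise.

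**What to change.** 1. In Table 2-3, define average dose, planned and actual, as cumulative dose divided by overall drug exposure. Sum over dosing records, each contributing its dose times its own number of days, with 0 mg records between first and last dose counted as zero. This needs SAP wording and programming only, because the record form already collects the start and end date of each dose (SAP 2.3.3.1).

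2. Footnote the AE, serum creatinine and creatinine clearance tables by average actual dose, to say that dose changes made in response to events affect group membership and that the split is not a dose-response comparison. This costs nothing beyond the text.

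3. Optional: tabulate AEs by dose at onset with person-time at that dose. This means joining onset dates to dosing records. With at most 58 patients the tables would be sparse, would depend on imputed partial onset dates, could not place AEs with no onset date, and would still be observational. They would not address the creatinine tables.

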5.1.4.2 Dose interruptions, dose delays, and dose changes

This section provides additional details to those included in Section 2.5.1.

Dose interruption

A dose interruption will be indicated in the eCRF by a dosing record with an actual total daily dose of 0 mg for one or more days. In order not to over count interruptions, dosing records with 0 mg entered as last dosing record will not be counted as interruptions. Those represent the reason for permanent discontinuation and will therefore be presented in the reason for treatment discontinuation analysis.

Dose reduction

A reduction is defined as a decrease from the previous non-zero dose. For example, in the sequence of planned dose (mg/kg/day) 25-0-15, the 15 mg/kg/day dose will be counted as a reduction. The planned zero dose is also counted as a dose reduction record. The reduction will be determined using the eCRF 'planned dose'. If the planned dose is reduced as described above, a reduction will be counted.

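### SAP 2.5.1 and 5.1.4.2 use different comparators for planned dose changes, so a restart after a planned zero can be tabulated as an increase and a permanent stop as a reduction

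*SAP*

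**What the plan says.** Protocol 10.3 asks for the frequency of interruptions, decreases and increases in planned dose, overall and by reason. SAP 2.5.1 turns this into numbers and percentages of patients, each counted once per reason within reductions and within increases.

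The rules in SAP 2.5.1 are:
- Reduction: "A planned dose reduction is when a planned dose is lower than the previous planned dose", with the addition that "a planned zero dose is included as a dose reduction record".
- Increase: "A planned dose increase is when a planned dose is higher than the previous planned dose".
- Interruption: "A dose interruption is when an actual dose is recorded as zero". This rule uses the actual dose, not the planned dose.

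SAP 5.1.4.2 presents itself as further detail on 2.5.1. It measures a reduction from the previous non-zero dose and gives an example: "in the sequence of planned dose (mg/kg/day) 25-0-15, the 15 mg/kg/day dose will be counted as a reduction". It repeats that a planned zero is a reduction. Under the heading for interruptions, which are again defined on actual dose, it adds that "dosing records with 0 mg entered as last dosing record will not be counted as interruptions", because such records stand for permanent discontinuation. It contains no rule for increases. SAP Section 4, which lists changes from the protocol's analyses, does not mention the difference.

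**The concern.** The two sections compare a restart dose with different things. One compares it with the zero just before it, the other with the last dose actually planned above zero. A programmer who follows 2.5.1 literally and one who follows 5.1.4.2 will classify the same record in opposite directions. A programmer who treats 5.1.4.2 as a supplement will find that the record meets both definitions.

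Three kinds of event that the protocol wants kept apart can therefore be blended. A restart after an interruption can appear beside escalation for ferritin control. A temporary stop or a permanent stop can appear beside a true step down. In a single-arm study whose primary objective is safety, these tables are part of how readers judge how the dose was tolerated and managed, so they should mean what their labels say.

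**Working it through.** There is no sample size or power figure to reproduce. The check applies the written rules to short planned-dose sequences (mg/kg/day).

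**The SAP's own example first.** For 25-0-15, SAP 5.1.4.2 compares 15 with 25. Since 15 < 25, the record is a reduction, which agrees with the stated result. SAP 2.5.1 compares 15 with 0. Since 15 > 0, the record is an increase.

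**Four ways of applying the rules**, shown as reduction records / increase records:
- A: 2.5.1 alone.
- B: the 5.1.4.2 reduction rule with the 2.5.1 increase rule, that is, 5.1.4.2 as a supplement.
- C: both directions compared with the previous non-zero dose, a planned zero still counted as a reduction.
- D: as C, but zeros left out of both counts.

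| Sequence | A | B | C | D |
|---|---|---|---|---|
| 25-0-15 | 1/1 | 2/1 | 2/0 | 1/0 |
| 25-0-25 | 1/1 | 1/1 | 1/0 | 0/0 |
| 21-0-21-0-21 | 2/2 | 2/2 | 2/0 | 0/0 |
| 28-0-14-28 | 1/2 | 2/2 | 2/1 | 1/1 |
| 14-0-17.5 | 1/1 | 1/1 | 1/1 | 0/1 |
| 21-0 (final record) | 1/0 | 1/0 | 1/0 | 0/0 |

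**From records to patients.** The SAP tabulates patients, so what matters is whether a patient has at least one reduction or increase. Assume the sequence shown is the patient's whole dosing history.
- 25-0-25 (and its repeat with 21): flagged as increased under A and B, not under C or D. The reduction flag rests only on the planned-zero convention.
- 25-0-15: reduced under every version; flagged as increased under A and B only. The same holds for any restart below the earlier dose with no later rise.
- 21-0: flagged as reduced under A, B and C, although the only event is a permanent stop.
- 28-0-14-28: reduced and increased under all four versions, so the overall flags do not move. Only the rows by reason could change, if the reason recorded for the 14 differs from that for the 28.
- 14-0-17.5: the increase is real under every version.

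The sections point in opposite directions only for restarts below the last non-zero dose. For a same-dose restart, 2.5.1 finds an increase and 5.1.4.2 finds no reduction at the restart.

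**Are such sequences foreseen?** SAP 5.1.4.2 uses a planned zero in its own example. Protocol 6.3.1.2, after an interruption for creatinine, says "it is recommended to resume therapy at 50% of the last dose", and 6.3.1.5 describes a comparable restart after rash. Protocol 6.3.1.3 (low ferritin) and 6.3.1.4 (proteinuria) foresee interruptions without stating the restart level. None of this says whether sites enter the planned dose as zero in the meantime.

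**Weight of one patient.** SAP Section 3 plans at most 58 patients. 1/58 = 0.0172, so one misclassified patient moves a percentage by at least 1.7 points.

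**The case against.** The strongest defence has four parts.

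First, counting a planned zero as a reduction is deliberate: both sections state it. That stands, and the convention is not an error in itself. It does not explain the false increase, which comes from using zero as the comparator in 2.5.1.

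Second, interruptions are defined on actual dose, and planned and actual dose are recorded separately. If sites enter zero only as the actual dose, no false reduction or increase arises. This also stands. It limits how often the problem occurs, but leaves the rule unclear where a planned zero is entered. By the same token, the exclusion of final 0 mg records is written under a definition based on actual dose. It is therefore not an explicit rule for planned zeros that the SAP breaks. The gap is that its rationale, permanent discontinuation, applies equally to a final planned zero and was not carried across to reductions.

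Third, the tables are descriptive exposure summaries. The primary variables in SAP 2.6.1 are treatment-emergent adverse events and laboratory changes, and SAP 2.9.1 summarizes separately the adverse events leading to discontinuation, dose adjustment or interruption. None of these uses the dose-change derivation. Reasons and patient listings also help a careful reader separate restarts from escalation.

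Fourth, patients who complete the protocol's path of restarting at half dose and returning to the earlier dose have a genuine reduction and a genuine increase. A reader might infer from the record counts for 28-0-14-28 that such patients are misclassified. At patient level their overall flags are the same before and after correction.

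**Conclusion.** The inconsistency is real and is shown by the SAP's own example: one record is an increase under 2.5.1 and a reduction under 5.1.4.2. Followed literally, 2.5.1 gives wrong patient counts in two settings: restarts at the same dose, and restarts at a lower dose with no later rise. Separately, a final planned zero adds a reduction for a patient whose only event was a permanent stop.

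The size cannot be estimated, because the documents do not say how often the planned dose is entered as zero. A reader might infer that nearly every interrupted and restarted patient will appear as increased. That would follow only if a planned zero were entered each time, which the documents do not establish. Nor do they support a claim that the primary safety, average-dose or ferritin results are affected. The consequence is confined to the dose-change tables and their rows by reason, but it is worth correcting because two programmers could produce different tables from the same text.

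**What to change.** Use one rule in SAP 2.5.1 and 5.1.4.2:
1. Compare each non-zero planned dose with the last preceding non-zero planned dose. Lower is a reduction, higher is an increase, equal is neither.
2. Do not count a planned zero that is the last dosing record as a reduction. Treat it as permanent discontinuation, as 5.1.4.2 already does for final 0 mg records in the interruption count.
3. If a planned zero that is not the last record continues to count as a reduction, show those patients on a separate row, so that they are not mixed with reductions to a lower non-zero dose. Keeping or dropping that convention is the sponsor's choice.

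With this rule, 25-0-15 gives one reduction to a lower non-zero dose and no increase. 25-0-25 gives neither, with the zero on its own row if the convention is kept. 28-0-14-28 gives one reduction to a lower non-zero dose and one increase.

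The cost is SAP wording and one derivation. No new data are needed and no dosing rule changes. The reported counts of increases and reductions may fall.
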